The objective of this grant-funded proposal (R01CA184781) is to determine the feasibility of smartphone-delivered, in-home ABM to reduce AB to smoking cues and to reduce smoking behavior in the short- and long-term. Participants will be 250 treatment-seeking smokers, who will receive 8 weeks of nicotine replacement therapy (NRT) after completing either ABM (AB away from smoking cues and toward neutral cues) or sham training. Smokers will attend 3 sessions. The 1st lab session will establish each smoker's baseline smoking behavior and AB towards smoking picture and word cues by assessing reaction time (RT) and event-related potential (ERP) electroencephalography to modified dot-probe (MDP) and Stroop color-word naming tasks. After the 1st lab session, participants will complete 13 days of daily in-home training (ABM or sham), assessments to track changes in AB, and ratings of smoking behavior and craving, that will be administered through provided smartphones, with compliance and ABM accuracy rewarded monetarily. The 2nd lab session will occur immediately after the 2 weeks of in-home training and will involve the same assessments as the 1st session, to gauge the short-term impact of ABM on AB and smoking behavior. All participants will then receive counseling and the first half of an 8-week supply of NRT to quit smoking. The 3rd lab session, which will occur after NRT, will evaluate the longer-term impact of training on smoking behavior and AB. We propose the following specific aims and hypotheses that will address PQA3 of this RFA:

Aim 1: Identify the impact of in-home ABM on AB. We hypothesize that 2-wk in-home ABM, compared to sham training, will decrease AB towards smoking cues and increase AB towards neutral cues, as measured by RT to the MDP and Stroop tasks. We hypothesize that the changes in AB will generalize to novel and cross-modal stimuli. We hypothesize that short-term changes in AB will also be present at 8 weeks following the completion of training.

Aim 2: Identify the impact of in-home ABM on smoking behavior. We hypothesize that 2-wk in-home ABM, compared to sham training, will result in fewer cigarettes (including little cigars) smoked per day, lower expired carbon monoxide, lower urine cotinine values, decreased craving to smoke, and lower nicotine dependence after 8 weeks of NRT.

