participants will be trained in the use of the smartphone. They will be told that the in-home smartphone ABM training will help them prepare to quit, and that their quit dates will be scheduled for the day after Laboratory Session 2. The participants will be instructed that they can, but are not required to, reduce or eliminate their smoking before their quit date. During the in-home ABM training sessions, participants will complete daily 30-minute training (ABM or sham) and AB assessment sessions on their provided smartphone for 13 days. The 13-day training period was selected because two weeks of in-home training reduced AB in an anxiety study [48]. Participants will be trained on the ABM tasks at the end of the baseline session. The participants will be instructed to complete the task in a quiet, well-lit location in their homes, free from distraction and interruption, at approximately the same time each day. Compliance and accuracy on the training and assessment tasks will be tracked by the program and rewarded by on-screen tallies of money earned at the end of each ABM block. Participants who fail to complete a training and assessment session, or who do so poorly (25% or more incorrect), will receive a message (SMS text or phone call, depending on participant preference) reminding them to complete the training and/or assessment tasks accurately the next day. If a participant fails to complete the task for 2 or more consecutive days, or has 25% or more errors during a training session, a staff member will call him or her to troubleshoot any impediments and encourage training participation.

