The smartphone-delivered ABM and sham training (Figure 4) will both involve the same MDP task timing, scoring, and monetary reinforcement schedule as the laboratory AB assessment, with several exceptions. First, the ratio of probes following each picture type will differ by ABM group. In the ABM group, 100% of the probes will replace neutral pictures, to reduce participants' AB to smoking cues, while in the sham group, probes will follow each of the 2 picture types an equal number of times, to avoid influencing AB. Second, the training groups will both involve more blocks of trials than the AB assessment, consistent with other ABM studies [2]. The ABM training session will consist of 22 picture pairs repeated 20 times over 8 blocks, for a total of 440 trials, 55 per block. Third, the task will be presented over the smartphone, with no EEG collected. Each picture will be 5 cm wide by 5 cm high, and the response will be considered correct if the participant taps within this region on the side of the screen where the probe is presented. The maximum performance bonus for the MDP task for each session is \$11 (\$0.025 per trial). The in-home ABM training will last for approximately 20 min.

[figure not shown]
In-Home Smartphone: AB assessment using the Stroop. After completing the last block of ABM or sham training, participants will immediately and seamlessly transition to the in-home AB assessment component. The in-home AB assessment will use the Stroop task. The in-home Stroop task will be identical to the laboratory task, except that it will be given over the smartphone. Thus, the 4 response buttons will be presented on the touch screen, 2 each to the left and right of the word (**Figure 5**). The placement of the buttons on the left and right side of the screen will allow for participants to respond quickly with their thumbs. The color assigned to each of the four buttons will be randomly varied from day to day. The word will be presented in the center of the screen, approximately 4 cm wide and 2 cm high. Each button will be 3 cm wide by 3 cm high. The in-home AB assessment will take approximately 7 min to complete. The maximum performance bonus for the Stroop task for each session is \$4 (\$0.025 per trial).

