
Statistical Approach & Expected Outcomes

Aim 1. Identify the impact of in-home ABM on AB. We will evaluate this aim using 2 (group: ABM vs. sham) X 3 (session: baseline, 1-day post-training, and 8-weeks post-training) linear mixed model using RT difference scores (neutral-cigarette) as the dependent measures and subject as the random effect. We will conduct separate analyses on the dependent measures (within-modality: MDP RT difference scores; between-modality: Stroop RT difference scores) collected at baseline, 1-day post-training, and 8-weeks post-training. We predict that post-training AB scores, calculated from RT, will decrease from baseline for those in the ABM training, but not in the sham training condition, indicating a reduction in AB to smoking cues.

Aim 2. Identify the impact of in-home ABM on smoking behavior. We will evaluate this aim using two types of models. For the continuous (i.e., normally distributed) measures of smoking behavior, we will conduct mixed between-within repeated measures ANOVA using the same predictors and covariates as are described in Aim 1. Separate analyses will be run for each of the continuous dependent measures, including mean CPD over the past 7 days, expired CO, cotinine, FTND, and WSWS Craving. We expect that ABM training, compared to sham training, will decrease measures of smoking exposure (CPD, expired CO, cotinine), levels of dependence (FTND), and levels of craving (WSWS Craving) at the 1-day and 8-weeks post-training sessions. For the categorical variable of 8-weeks post-NRT abstinence, we will conduct a chi-square test of independence on the 2 (abstinent vs. nonabstinent) x 2 (ABM vs. sham training) table. We expect that ABM training, compared to sham training, will result in a higher rate of abstinence.

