Exploratory analyses. We will examine the Aim 1 and 2 models covarying the total number of completed ABM or sham training sessions, the number of in-home training sessions completed, in-home training sessions accuracy rates, baseline FTCD, sex at birth, and CPD at each session. We will conduct the following exploratory analyses using multilevel modeling: (1) We will examine the impact of ABM on AB, CPD, and craving assessments collected by smartphone to determine whether the optimal length of training is less than 13 days; (2) We will examine whether individual differences, measured at baseline, predict response to the ABM training on our measures of AB and smoking behavior. These individual differences will include baseline levels of nicotine dependence (i.e., FTND, mCEQ, CPT, and WSWS), mood (i.e., PANAS), anhedonia (i.e., SLIPS), impulsivity (i.e., DDT, SUPPS-P), tolerance to stressors (i.e., DTS and ASI), reward sensitivity (i.e., Passive Picture Viewing), smoking exposure (i.e., CPD and expired CO), gender, handedness (i.e. Chapman Handedness questionnaire), and AB to smoking cues; (3) We will examine whether participants' contingency awareness of the ABM task influenced ABM's effectiveness, because one ABM study with smokers found that only those participants who were aware of the relationship between the probe and stimulus type were responsive to ABM [7]; (4) We will use data about the training environment collected using the smartphone (e.g., location, dB levels, ambient lighting) to examine whether these environmental characteristics influenced ABM's effectiveness; (5) We will use the EEG data collected using our 129-channel sensor net to perform event-related potential (ERP) analyses (including the P1 component), along with source localization analysis to attempt to identify areas in brain that are responsive to ABM. We will preliminarily target occipital regions that have been found to activate in the presence of motivationally salient visual cues [91,124]. (6) We will examine the effects of AB on eye-tracking metrics (e.g., fixation, gaze duration) and compare the reliability of eye tracking with traditional reaction time metrics of AB.

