Power analysis. To demonstrate that this proposal has adequate sample size to detect meaningful amplitude changes in the continuous measures taken at the post-training laboratory sessions (Specific Aims 1 & 2), we conducted a power analysis using the G*Power program (v3.1.2; Heinrich Heine University, Düsseldorf, Germany). We calculated power to ensure that we could detect a significant 2-way (ABM intervention by time) ANOVA interaction for any of our continuous measures, as assessed at the baseline, 1-day post-training, and 8-weeks post-training sessions. If we assume a conservative Bonferroni-corrected Type I error rate of $\alpha=0.01$, 250 participants, moderately correlated within-subject observations ($r=0.5$), and a conservative nonsphericity correction ($\varepsilon=0.75$) we have 80% power to detect differences corresponding to a Cohen's f of 0.11 or larger for the 2-way interaction. Even if we were to experience an unlikely 30% attrition rate, we would have power to detect a Cohen's f of 0.13 or larger. According to Cohen [117], a Cohen's f of 0.10, 0.25, and 0.40 correspond to a small, medium, and large effect size, respectively, meaning that we have the power to detect a small effect size or greater on our continuous measures. To demonstrate that we would have adequate power to detect likely AB differences for Aim 1, we searched the literature for studies with a similar design to ours. Given that no previous study has evaluated the impact of multi-session ABM on AB in

smokers, we decided to estimate a likely effect size from the one alcohol study that used the MDP task for both multi-session ABM and the AB assessments [2]. We estimated a Cohen's *f* value for this study by taking the square root of the *F* ratio multiplied by the ratio of the degrees of freedom [117]. From this formula, we estimated a Cohen's *f* of 0.64, based on the reported *F* value for the significant ABM training group (ABM, sham) main effect, $F(1,23)=9.4$, $p<.01$. This Cohen's *f* value corresponds to a large effect size and is well within the range for which we have sufficient power to detect. We recognize that this alcohol study does not provide an ideal comparison for the effects sizes we will likely obtain, but it does suggest that ABM produces large effects on AB, effects which should be well within the power requirements of our study to detect.

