In-home task compliance and accuracy. We expect high compliance and accuracy rates with the in-home ABM training and AB assessments. We were able to obtain compliance rates of 80% in a study in which we administered smoking cessation interventions and assessments with mobile phones to underserved persons living with HIV/AIDS, a high rate considering that many of them were homeless [56]. The only previous study to involve in-home ABM training, which was daily for 2 weeks, did not report a compliance rate, but did report an accuracy rate of 96% on the at-home ABM and AB MDP tasks [48]. Our ABM and AB tasks will have features designed to improve compliance and accuracy, including feedback after each block, and monetary incentives for task completion and accuracy. We will also have contingency procedures for contacting participants who do not comply with the in-home tasks, including email/texting and staff phone calls, if necessary. Compliance and accuracy rates will also be included in the statistical models used to evaluate our study aims.

[figure not shown]
AB assessment. The MDP and Stroop tasks that we are using to assess AB has been found to reliably detect AB across a variety of populations, including the healthy, the anxious, and the substance dependent. It has been found to be sensitive to multi-session ABM conducted with problem drinkers [29] and with the alcohol dependent [2,3]. Thus, we expect our AB tasks to be similarly reliable and sensitive to our ABM training. In terms of our exploratory ERP measure, the P1 ERP has been found to be a reliable indicator of AB in most [53,55,91] (but not all [118]) prior studies that evaluated P1 to a MDP task with motivationally relevant stimuli. However, if the P1 ERP is unable to distinguish AB, we would examine other ERP components, including the P2, N2, and the P3, all of which have been associated with later

stages of AB [118]. The P2 has been associated with attentional disengagement [119], the N2 with attentional control and inhibition [120], and the P3 with orienting of attention [121].

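### Analyse the continuous Aim 2 outcomes with the Aim 1 type of mixed model, with a stated covariate list, baseline adjustment and all retrieved data

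*Combined protocol and SAP*

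**What the plan says.** Under Statistical Approach & Expected Outcomes, Aim 1 is a group by session linear mixed model with a random subject effect. No covariate is named. For the continuous Aim 2 outcomes, "we will conduct mixed between-within repeated measures ANOVA using the same predictors and covariates as are described in Aim 1".

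Other sections bear on the same models:

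- Exploratory analyses: "We will examine the Aim 1 and 2 models covarying the total number of completed ABM or sham training sessions". The list goes on to accuracy, baseline dependence, sex at birth and CPD at each session. Gender also appears there as a predictor of response.
- In-home task compliance and accuracy (Potential Problems & Alternative Strategies): "Compliance and accuracy rates will also be included in the statistical models used to evaluate our study aims".
- Study overview: randomization is stratified by gender. After a missed Visit 3, staff seek a telephone TLFB for CPD and offer questionnaires by email.
- Power analysis: power is computed to "detect a significant 2-way (ABM intervention by time) ANOVA interaction for any of our continuous measures", over three sessions. For abstinence, missing participants count as smoking. No rule is given for missing continuous outcomes.
- Timing of the Aim 2 effect: the opening aims section predicts "decreased craving to smoke, and lower nicotine dependence after 8 weeks of NRT", while the Aim 2 analysis text expects lower "levels of craving (WSWS Craving) at the 1-day and 8-weeks post-training sessions".

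**The concern.** Two analysts could fit different main models from this text.

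**Missing data.** The standard between-within ANOVA needs every session from every participant, and the plan does not say whether it would be run that way. If it is, someone who misses Visit 3 also loses a usable 1-day value, and a telephone CPD value is used only if the analyst decides that it counts. Dropout in a cessation trial may also depend on relapse, so bias is at stake as well as precision.

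**Covariates.** The Aim 2 reference to Aim 1 covariates points to nothing, and the compliance section may or may not fill the gap. Compliance and accuracy are measured after randomization. Accuracy can itself be an effect of the arm: "In the ABM group, 100% of the probes will replace neutral pictures", whereas sham probes are split equally, so only in the ABM arm does the picture predict the correct response. Adjusting for it can remove part of the training effect. CPD at each session, another listed covariate, is itself an Aim 2 outcome.

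**Stratum.** Gender is absent from the main models. This is minor.

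**Working it through.** **Inputs from the Power analysis section:** N=250, alpha 0.01, 80% power, r=0.5, epsilon 0.75, 30% attrition (N=175). Equal arms and equal correlation between sessions are assumed below.

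**1. The plan's own figures.** For the two-arm, three-session interaction, lambda = f² × N × 3 × epsilon / (1 − r), with df 2 × epsilon and 2(N − 2) × epsilon. Solving for 80% power gives f = 0.1077 at N=250 and 0.1290 at N=175. These round to the stated 0.11 and 0.13, so both are correct.

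**2. Interaction in SD units.** For an arm difference d at one or both post-training visits, f = d/√18. At N=250 and r=0.5 the detectable d is 0.457 SD at epsilon 0.75 and 0.410 SD at epsilon 1.

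**3. Where a power gain comes from** (epsilon 1, noncentral t for single visits). A baseline-adjusted difference at one visit has variance (1 − r²) × 4/N; an unadjusted change score has 2(1 − r) × 4/N.

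| r (0.3 and 0.7 assumed) | Interaction | One visit, unadjusted change | One visit, baseline-adjusted |
|---|---|---|---|
| 0.3 | 0.485 | 0.515 | 0.415 |
| 0.5 | 0.410 | 0.435 | 0.377 |
| 0.7 | 0.318 | 0.337 | 0.311 |

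Naming a visit without baseline adjustment is worse than the interaction in every row. The gain from 0.41 to 0.38 SD is due to baseline adjustment and is almost nil at r=0.7.

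**4. Missing Visit 3.** Suppose all of the 30% attrition falls there: 75 of 250 missing, 175 complete. Detectable d = (2.576 + 0.842) × √variance (normal approximation), with baseline constrained equal across arms in the mixed model.

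- 1-day, complete cases: 0.75 × 4/175 = 0.0171, d = 0.447.
- 1-day, mixed model: 0.75 × 4/250 = 0.0120, d = 0.374.
- 8-week, complete cases: 0.0171, d = 0.447.
- 8-week, mixed model with n values at that visit: at r=0.5 the residual variance given both earlier sessions is 2/3, and the coefficient on the 1-day value is 1/3. The variance is therefore (2/3) × 4/n + (1/9) × 0.0120. With n=175 this is 0.0152 + 0.0013 = 0.0166, d = 0.440.
- 8-week CPD if telephone TLFB recovers an assumed 25/50/75% of the 75 missing (n = 193.75/212.5/231.25): variances 0.0151/0.0139/0.0129, d = 0.420/0.403/0.388.

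**5. Accuracy as a covariate.** In a baseline-adjusted contrast the arm effect shifts by the within-arm correlation times the arm difference in accuracy. For an assumed correlation of 0.1-0.3 and arm difference of 0.2-0.5 SD, that is 0.1 × 0.2 = 0.02 to 0.3 × 0.5 = 0.15 SD. Entered only as a constant main effect, accuracy would not move the interaction.

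**6. Gender.** If gender explains an assumed share R² of the variance and is left out, the true two-sided alpha of a baseline-adjusted contrast is 2 × (1 − Φ(2.576/√(1 − R²))). This gives 0.0093, 0.0082 and 0.0066 at R² = 0.02, 0.05 and 0.10, which is conservative. If the gender effect is constant over sessions, the interaction is unaffected.

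**The case against.** The strongest defence is that the plan has a valid test and has allowed for loss. The Power analysis section names the group by time interaction over three sessions and checks power at 30% attrition, so complete-case loss is budgeted. That stands for power but not for bias, and it does not settle how the outcomes are analysed. It is also true that at 8 weeks the mixed model alone gains almost nothing, and that nothing in the text excludes telephone values.

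On covariates, the compliance sentence may refer only to the re-runs that the exploratory section describes. That reading is possible but is not stated, and the harm from adjustment in step 5 rests on assumed inputs.

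Four stronger readings are tempting but not supported:

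- A reader might infer that the plan must name one decision visit. At r=0.5 and 0.374 SD, a baseline-adjusted test over both post-training visits has about 76% power if the effect is at either visit and about 89% if at both. One named visit has 79% if it is the right one and about 1% if the effect is only at the other.
- A reader might infer a contradiction on timing. The opening aims section itself gives Session 2 the purpose of gauging short-term impact on smoking behavior, so the Aim 2 hypothesis sentence is narrower than the design rather than opposed to it. The two visits do differ in kind, since before the 1-day visit "The participants will be instructed that they can, but are not required to, reduce or eliminate their smoking before their quit date". That is a reason to report both.
- A reader might infer that gender is ignored. It is in the exploratory analyses, both as a covariate (sex at birth) and as a predictor of response.
- A reader might infer that the power figures are wrong. They reproduce.

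**Conclusion.** The point holds as a gap in the specification of the main models. The continuous Aim 2 outcomes have an analysis that may discard data, no missing-data rule, and a covariate reference that leads nowhere, while two sections disagree on whether compliance and accuracy belong in the main models.

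The clearest cost is at the 1-day visit: 0.45 SD detectable with complete cases against 0.37 SD with a mixed model. At 8 weeks the benefit depends on using retrieved data, with 0.42-0.39 SD for CPD only against 0.447 SD. These sizes assume r=0.5, equal correlation between sessions, all 30% attrition at Visit 3, and the telephone recovery rates shown. The baseline-adjustment gain over the interaction is modest and shrinks as r rises. The gender omission is minor and errs on the conservative side. The interaction test remains valid.

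**What to change.** - Use the Aim 1 type of linear mixed model for every continuous Aim 1 and Aim 2 outcome, with baseline adjusted for or constrained equal across arms, gender as a fixed effect, and all available values, including telephone CPD and emailed questionnaires.
- List the main-model covariates. Reconcile the exploratory section with the compliance section so that compliance, accuracy and CPD at each session stay in exploratory models only.
- Keep a test of the arm effect over both post-training visits as the main test: the interaction or its baseline-adjusted two-visit form. Report the baseline-adjusted ABM versus sham difference at each visit. Do not require a single decision visit.
- Align the Aim 2 hypothesis sentence in the opening aims section with the Aim 2 analysis text.
- Use a gender-stratified Cochran-Mantel-Haenszel test for abstinence.
- Add a missing-data sensitivity analysis for CPD and CO, since dropout may depend on relapse and the mixed model alone would not remove that bias.

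The cost is minor SAP rewording and slightly more analysis work, with the same data, software and sample size.
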